1.0 Objectives

The primary objective of this pilot study will be to assess the safety of lenalidomide in combination with ipilimumab in autologous and allogeneic stem cell transplantation.

Secondary objectives include assessing:

1. Overall response rate
2. Overall survival, progression-free survival
3. Cumulative incidence of acute and chronic GVHD with the competing risk of relapse in allogeneic transplant patients.

2.0 Background

Relapse or progression of malignancy is an important cause of failure after hematopoietic stem cell transplantation. Adoptive immunotherapy can induce clinical responses in several malignancies.¹

Revlimid (Lenalidomide, LEN or IMiD3) is the leading compound among the immunomodulatory drugs or IMiDs.² It was developed as a structural analog of Thalidomide, from which it differs by the addition of an amino group and the removal of one of the carbonyl groups from the phthaloyl ring system. Thanks to these changes, LEN minimizes the toxicity typical of its parental drug, while optimizing therapeutic efficacy. This drug is now considered an emerging compound in hematologic malignancies.

The therapeutic efficacy of LEN is mainly associated with immunomodulatory, antiangiogenic, anti-inflammatory and, to a lesser extent, antineoplastic effects. The drug has indeed been shown to modulate several components of the immune system by restraining pro-inflammatory cytokine production, enhancing NK cell cytotoxicity and regulating T-cell proliferation. *in vitro* studies have demonstrated that LEN induces up to a 50 000-fold decrease in TNF- α , IL-1 β , IL-6, and IL-12 production by human peripheral blood mononuclear cells (PBMCs), whereas synthesis of IL-2 and IFN- γ was found to be dramatically increased.² T-cell proliferation, differentiation, and survival are primed by LEN via the B7-CD28 co-stimulatory pathway. Hayashi et al. have shown that incubation of PBMCs in the presence of LEN leads to an increase up to 1.5 times in NK cell number as compared to control cultures³. LEN has also been shown to significantly affect angiogenesis in various cancers, presumably by uncoupling angiogenesis from secretion of VEGF through inhibition of Gab1 and Akt phosphorylation, both proteins being recruited downstream of VEGFR stimulation.

Inadequate co-stimulation of T cells may be one mechanism underlying failure of adoptive immunotherapy. Expression of CTL4 is induced upon T cells upon activation. It competes with co-stimulatory receptor CD28 for the B7 ligands CD80 and CD86 on antigen-presenting cells. Through this and other mechanisms, CTLA4 functions as an important negative regulator of the duration and intensity of antigen-specific T-cell responses.⁵ CTLA4 is an important mediator of peripheral self-tolerance and tolerance to tumor antigens. Ipilimumab

is a fully human immunoglobulin G1 (IgG1) monoclonal antibody that antagonizes CTLA4. The rational for using anti-CTLA4 is to un-restrain pre-existing anticancer T-cell responses (in this case, induced by LEN) and possibly trigger new responses. This is the reason why this clinical trial with Ipilimumab is so important, especially now that Ipilimumab has been approved by the U.S. Food and Drug Administration for the treatment of metastatic melanoma. The assessment of the potentiating effect of Ipilimumab on the immunomodulatory effects of LEN will open new treatment options for lymphoid and other hematologic malignancies.

Three published studies have established the safety of ipilimumab after allogeneic stem cell transplantation.⁵⁻⁷ The dose of 3.0 mg/kg iv every 3 to 4 weeks x 4 was not associated with significant toxicity.⁵⁻⁷ We are proposing the same dose level in this pilot study.

The use of LEN after allogeneic stem cell transplantation has also been studied at MD Anderson using protocol 2007-0871. No patient in that trial died of graft-versus-host disease (GVHD) induced or related to LEN.

3.0 Eligibility

3.1 Inclusion Criteria

- a. Age \geq 18 years to \leq 80 years.
- b. Hematologic or lymphoid malignancy.
- c. Autologous patients can be included anytime within 6 months post-transplant, if they had no signs of progression and meet one of the following criteria:⁸⁻⁹
 - i. Leukemia
 - ii. Lymphoma (all types of B and T cell lymphoma)
 - iii. Multiple myeloma
- d. Allogeneic patients if:
 - i. Patients had engrafted donor cells (i.e., > 20% donor T-cell from PB/PCR); and,
 - ii. Patients NOT in CR after their allogeneic transplant, and off tacrolimus and/or mycophenolate mofetil for at least 3 to 4 weeks with no signs of GVHD; or,
 - iii. Patients had evidence of relapse after their transplant who are off tacrolimus and/or mycophenolate mofetil or other immunosuppressants for GVHD for 3 to 4 weeks with no signs of GVHD (Prednisone doses \leq 10 mg are permitted as stated previously).
- e. No active infection.
- f. ANC \geq 1.5 x 10⁹/L; platelets \geq 50 x 10⁹/L.
- g. Able to adhere to the study visit schedule and other protocol requirements.
- h. Performance status: ECOG 2 or less or Karnofsky of at least 60.
- i. Cardiac EF \geq 45% by 2D-ECHO within 3 months of study entry (or within 1 month if received chemotherapy within the past 3 months).
- j. FEV1, FVC and DLCO \geq 40% within 3 months of study entry (or within 1 month if received chemotherapy within the past 3 months).
- k. Serum creatinine \leq 1.6 mg/dL and creatinine clearance \geq 30 ml/min. Creatinine clearance will be calculated using the Cockcroft-

Gault equation: Use actual body weight if it is less than or equal to ideal body weight. Use ideal body weight if patient greater than ideal body weight, but is less than or equal to 50% over ideal body weight. Use adjusted body weight if patient is greater than 50% over ideal body weight.

- I. Liver function tests (unless related to Gilbert's disease or medications)
 - i. SGPT, SGOT less than 2x the upper limit of normal range.
 - ii. Direct Bilirubin <1.6
- m. Patient or legally authorized representative able to sign informed consent.
- n. Females of childbearing potential (FCBP)† must have a negative serum or urine pregnancy test with a sensitivity of at least 50 mIU/mL within 10 - 14 days prior to study entry.

3.2 Exclusion criteria

- a. Immunotherapy or chemotherapy with approved or investigational anticancer therapeutics within 4 weeks of first dose.
- b. Patients on alemtuzumab within 6 weeks prior to consenting.
- c. Active congestive heart failure (NYHA Class III to IV), symptomatic ischemia or conduction abnormalities uncontrolled by conventional interventions. Myocardial infarction within 6 months of study entry.
- d. Deep vein thrombosis or pulmonary embolism within 3 months of study entry.
- e. Pregnant or breast-feeding females. (Lactating females must agree not to breast-feed while taking lenalidomide).
- f. Acute active infection requiring intravenous antibiotics, antiviral (except antiviral directed at hepatitis B), or antifungal agents within 14 days of first dose.
- g. Known HIV seropositive, hepatitis C infection, and/or hepatitis B (except for patients with hepatitis B Sag or core antibody receiving and responding to antiviral therapy directed at hepatitis B: these patients are allowed).
- h. Patients with other known malignancies within the past three years except:
 - i. Adequately treated basal or squamous cell skin cancer.
 - ii. Carcinoma in situ of the cervix.
 - iii. Prostate cancer with Gleason score < 6 with stable PSA over the past three months.
 - iv. Breast cancer in situ with full surgical resection.
 - i. Significant neuropathy (grades 3 to 4 or grade 2 pain).
- j. Known hypersensitivity to thalidomide, lenalidomide or ipilimumab.
- k. Active life-threatening autoimmune disease.
- l. Active GVHD or recent GVHD and still on > 10 mg prednisone (or equivalent).
- m. Prior auto-immune disease.

4.0 Treatment Plan

Eligible patients will receive lenalidomide alternating with ipilimumab for 8 cycles.

Patients who are still receiving or just finished (i.e., within 3 months) the original treatment plan will be re-consented to receive 4 additional cycles (i.e., 8 total cycles).

Lenalidomide will be given daily for 21 days (Cycle 1). One dose of ipilimumab (Cycle 2) will be given within 1-3 days from the last day of lenalidomide, then followed by 4 weeks of rest.

Repeat lenalidomide daily for 21 days (Cycle 3) followed by one dose of ipilimumab (Cycle 4) within 1-3 days from the last dose of lenalidomide. Treatment will be repeated for a total of 8 cycles.

Creatinine Clearance (mL/min)	Cycles 1, 3, 5, 7	Cycles 2, 4, 6, 8
Greater than 60	Lenalidomide 10 mg PO daily for 21 days	Ipilimumab 3 mg/kg IV x 1 dose (given 1-3 days after lenalidomide, then followed by 4 weeks of rest)
30 to 60	Lenalidomide 5 mg PO daily for 21 days	Ipilimumab 3 mg/kg IV x 1 dose (given 1-3 days after the last dose of lenalidomide)

Creatinine clearance. Use Cockcroft-Gault formula and ideal body weight (IBW) as described above in inclusion criteria (Section 3.1)

If the starting combination of lenalidomide 10 mg/day alternating with ipilimumab 3 mg/kg results in toxicity in the first 3 of 3 patients (as defined in toxicity monitoring rule) then subsequent patients will be started at a lower combination dose of lenalidomide 5 mg/day (or 5 mg every other day for creatinine clearance of 30 to 60 ml/min) and ipilimumab 3 mg/kg.

4.1 Management of Immune-Mediated toxicity from ipilimumab:

There are no dose reductions for Ipilimumab. The only modifications to drug are to pause until improvement or stop.

Signs and Symptoms	Assessment of cause and severity	Procedure for adverse effects	Ipilimumab therapy
Gastrointestinal Colitis, diarrhea, blood in stool and/or abdominal pain	Exclude other causes (disease progression, GVHD, infection) Measure AE severity using NCI-CTCAE v3.0 (diarrhea/colitis severity grading scale 3)	Mild (grade 1,2): - Symptomatic therapy	Continue therapy
		Mild (grade 2) with longer term symptoms (5-7 days): - Corticosteroid therapy with prednisone 1 mg/kg/day (or equivalent)	Pause therapy until improvement to ≤ grade 1 STOP
		Symptom improvement: taper drug over 4 weeks	
		Severe (grade 3,4) or no improvement after 5 days on steroid (grade 2) or relapse after steroid taper: - Methylprednisolone 2 mg/kg/day IV	
		Symptom improvement: taper drug over 4 weeks	
		Severe (grade 3,4) and no improvement after 5 to 7 days of steroid or relapse after reducing steroids: - Consider adding other immunosuppressant's (i.e. infliximab 5mg/kg IV or other agents per departmental GVHD standard of care).	STOP
		Infliximab is contraindicated in bowel perforation or sepsis.	
Hepatitis Increased liver values (> 2.5x ULN or > 2 x baseline)	Rule out other causes (medication, infection, GVHD) Close control of liver values (assess every 3 days)	Other causes (not believed to be ipilimumab and not from GVHD)	Continue therapy
		Liver values ≥ 2.5 x to 8 x ULN: - Daily LFTs on 3 consecutive days. If no improvement steroid therapy	Pause therapy until LFTs back to normal or ≤ 2.5x ULN STOP
		Liver values > 8 x ULN or total bilirubin > 5 x ULN: - Methylprednisolone 2 mg/kg/day IV. Daily LFTs for 5 days, then every 3 days thereafter.	
		Once LFTs are under control: taper steroid over at least 4 weeks and check LFTs weekly	
		Persistently high LFTs after 3 to 5 days or a new increase in LFTs during steroid reduction: - Consider adding additional immunosuppressant drugs (i.e. mycophenolate mofetil 15 mg/kg IV/PO every 8 to 12 hours)	
Dermatitis Skin eruptions and psoriasis	Perform skin biopsy to rule out GVHD in allogeneic patients	Grade 1,2: - Topical management (topical corticosteroid and/or topical anti-pruritic)	Continue therapy
		Grade 3 or persistent grade 2: - Corticosteroid therapy with prednisone 1 mg/kg/day (or equivalent)	Pause
		Symptom improvement: taper drug over 4 weeks	
		Grade 4 (i.e. Stevens-Johnson Syndrome, toxic epidermal necrolysis): - Methylprednisolone 2 mg/kg/day IV	STOP
		Taper over a MINIMUM of 4 weeks	

Signs and Symptoms	Assessment of cause and severity	Procedure for adverse effects	Ipilimumab therapy
Endocrine Headache, vision field disturbance, fatigue, loss of appetite, nausea and vomiting, lethargy, impotence, amenorrhea, fever, coma, onset of heart flutter, hypotension, hypoglycemia, hypotremia , eosinophilia	If no suspected adrenal insufficiency: 1. TSH, Free T4 and ACTH 2. MRI of the head with hypophysis, possible vision field testing 3. Endocrine consultation	No abnormal results: - Rule out other causes, - Repeat labs in 1-3 weeks - Frequent follow up	Continue therapy
	Suspected adrenal insufficiency: - Therapy for adrenal insufficiency - Exclude sepsis	Abnormal results: - Short term (7 days) high dose mineral corticoids against inflammation (i.e. dexamethasone 4 mg IV or PO every 6 hours) - Hormone substitution therapy against endocrinopathy - Endocrine consult Taper high dose steroid over at least 4 weeks and continue hormone substitution if necessary. Repeat MRI depending on clinical signs Antimicrobial prophylaxis per departmental standard of care (as applicable to patients with acute GVHD on steroids)	Grade 2 – Pause and resume upon symptom improvement Grade 3,4 - STOP
Neuropathies Assessment of neuropathy Sensory symptoms constant for ≥ 5 days Motor testing	Rule out inflammatory causes (i.e. infection, metabolic, other drugs) Neurological consult, EMG and nerve conduction studies, comprehensive testing of neurologic syndrome and measurement of baseline values to assess development	Grade 1: - Treat symptoms based on recommendations from Neurology consult - If related to ipilimumab, possible IV steroids for grade 3,4 AEs Grade 2: - Treat symptoms based on recommendations from Neurology consult - If related to ipilimumab, possible IV steroids for grade 3,4 AEs Grade 3,4 sensory or clinically stable motor: - Treat symptoms based on recommendations from Neurology consult - If related to ipilimumab, possible IV steroids for grade 3,4 AEs Grade 3,4 motor and not clinically stable: - If atypical or progressive, admit to hospital and give IV steroids (methylprednisolone 2 mg/kg/day) - Possible IVIG or other immunosuppressants	Continue therapy Pause (if related) STOP STOP

In all patients who receive corticosteroids to treat/manage ipilimumab AEs, antimicrobial prophylaxis should be given for prevention of herpes infection, bacterial infection, fungal infection and PCP pneumonia as per departmental standard of care (as applicable to allogeneic patients with acute GVHD on steroids)

4.2 Ipilimumab specific requirement/toxicity management

1. Liver toxicity
 - a. Monitor liver function and evaluate for signs of hepatotoxicity prior to each dose (cycles 2, 4, 6, and 8). If hepatotoxicity develops, liver function should be monitored frequently until resolution.
2. Other monitoring
 - a. Monitor serum chemistries before each dose
 - b. Monitor for signs of hypophysitis, adrenal insufficiency and thyroid disorders
 - i. Abdominal pain, fatigue, headache, hypotension, mental status changes, unusual bowel habits
 - c. TSH, free T4 and total cortisol level should be checked at baseline, prior to each dose and as clinically indicated
 - d. Monitor for signs or symptoms of enterocolitis
 - e. Monitor for signs of motor or sensory neuropathy
 - f. Monitor for ocular toxicity at baseline then and before each dose

4.3 Lenalidomide specific requirements/toxicity management

1. Females of childbearing potential (FCBP)† must have a negative serum or urine pregnancy test with a sensitivity of at least 50 mIU/mL within 10 – 14 days prior to and again within 24 hours of the first dose of lenalidomide in Cycles 1, 3, 5, and 7 and must either commit to continued abstinence from heterosexual intercourse or begin TWO acceptable methods of birth control, one highly effective method and one additional effective method AT THE SAME TIME, at least 28 days before she starts

taking lenalidomide. FCBP must also agree to ongoing pregnancy testing. Men must agree to use a latex condom during sexual contact with a FCBP even if they have had a successful vasectomy. See Appendix C: Risks of Fetal Exposure, Pregnancy Testing Guidelines and Acceptable Birth Control Methods.

- a. All study participants must be registered into the mandatory Revlimid REMS™ program, and be willing and able to comply with the requirements of the Revlimid REMS™ program.
- b. Prescriptions must be filled within 7 days.

2. Dosing Regimen: Patients will be given a pill diary for Cycles 1, 3, 5, and 7 in order to document self-administration of the lenalidomide.
 - a. The drug will be given in the morning at approximately the same time each day for a total of 21 days (which should be consecutive, unless held for toxicities as described in the table below). Only enough lenalidomide for 21-days of therapy will be supplied to the patient.
 - b. Lenalidomide capsules should be swallowed whole, and should not be broken, chewed or opened.
 - c. If a dose of lenalidomide is missed, it should be taken as soon as possible on the same day. If it is missed for the entire day, it should not be made up.
 - d. Patients who take more than the prescribed dose of lenalidomide should be instructed to seek emergency medical care if needed and contact study staff immediately.
 - e. Subjects experiencing adverse events may need study treatment modifications
 - f. Special Handling Instructions
 - g. Females of childbearing potential should not handle or administer lenalidomide unless they are wearing gloves.

NCI CTC Toxicity Grade	Action
Grade 3 neutropenia associated with fever (temperature $\geq 38.5^{\circ}\text{C}$) or Grade 4 neutropenia (ANC $\leq 500/\text{mm}^3$, $\leq 75\%$ of baseline)*.	
 1) Hold (interrupt dose). 2) Follow CBC weekly until resolution or stabilization 3) If neutropenia has resolved to \leq grade 2, implement one dose reduction and continue therapy. 4) If neutropenia is the only toxicity for which a dose reduction is required, GCSF may be used and the lenalidomide dose maintenance.
Thrombocytopenia Grade 4 (platelet count $\leq 25,000/\text{mm}^3$)*.	
 1) Hold (interrupt dose). 2) Follow CBC weekly until resolution or stabilization 3) If thrombocytopenia resolves to \leq grade 2, implement one dose reduction and continue therapy.
Non-blistering rash Grade 3	
 1) If grade 3, hold (interrupt) dose. Follow weekly until resolution or stabilization. 2) If the toxicity resolves to \leq grade 1, implement one dose reduction and continue therapy.
Grade 4	1) Discontinue lenalidomide study drug.
Desquamating (blistering) rash-any Grade	Discontinue lenalidomide study drug.
Erythema multiforme Grade 3	Discontinue lenalidomide study drug.
Neuropathy Grade 3	
 1) If grade 3, hold (interrupt) dose. Follow weekly until resolution or stabilization. 2) If the toxicity resolves to \leq grade 2, implement one of dose reduction and continue therapy.
Grade 4	Discontinue lenalidomide study drug.
Sinus bradycardia/other cardiac arrhythmia Grade 2	
 1) Hold (interrupt dose). Follow at least weekly until resolution or stabilization. 2) If the toxicity resolves to \leq grade 1, implement one dose reduction and continue therapy.
\geq Grade 3	Discontinue lenalidomide study drug.
Allergic reaction or hypersensitivity Grade 3	
 1) Hold (interrupt dose). Follow at least weekly until resolution or stabilization 2) If the toxicity resolves to \leq grade 1, implement one dose reduction and continue therapy.
Grade 4	Discontinue lenalidomide study drug.

NCI CTC Toxicity Grade	Action
Venous thrombosis/embolism =/= Grade 3	Hold (interrupt) dose and start anticoagulation; restart at investigator's discretion (maintain dose level).
Hepatic or other non-hematologic toxicity assessed as lenalidomide-related =/= Grade 3	1) Hold (interrupt) dose. Follow at least weekly until resolution or stabilization. 2) If the toxicity resolves to </= grade 2, implement one dose reduction and continue therapy.
Tumor flare refractory to oral pain meds and/or antihistamines	Hold dose and differentiate tumor flare from progression. Restart therapy at the investigator's discretion.

4. Treatment and Dose Modification for Tumor Lysis Syndrome for Patients receiving Lenalidomide

- All subjects meeting criteria of laboratory TLS or >/= Grade 1 TLS according to the Cairo-Bishop Definition of Tumor Lysis Syndrome (see Appendix D) should receive vigorous intravenous hydration and should be considered for rasburicase therapy as needed to reduce hyperuricemia, until correction of electrolyte abnormalities.
 - In cases of laboratory TLS and Grade 1 TLS (see Appendix D: Cairo-Bishop Definition of Tumor Lysis Syndrome), lenalidomide will be continued at the same dose without interruption or dose reduction. TLS prophylaxis measures outlined in Lenalidomide Maintenance should be continued or re-instituted.
 - Subjects with >/= Grade 2 TLS (see Appendix D: Cairo-Bishop Definition of Tumor Lysis Syndrome) will be managed as follows in addition to intravenous hydration and consideration for rasburicase therapy (above).
 - Hold (interrupt) treatment.
 - First episode: restart lenalidomide at the current dose with appropriate TLS prophylaxis after resolution of electrolyte abnormalities to Grade 0
 - Subsequent episodes: restart lenalidomide with appropriate TLS prophylaxis after resolution of electrolyte abnormalities to Grade 0. At physician discretion, the lenalidomide dose may be restarted at the current dose or lenalidomide may be reduced by 1 dose level.
 - First or subsequent episodes: subjects should be closely monitored for signs of TLS after resuming treatment. To monitor for TLS, serum chemistry and uric acid tests should be performed at least every week following initiation of lenalidomide for 4 consecutive weeks and on Day 3 or 4 following initiation of lenalidomide.

5. Tumor Flare Reaction (TFR)

- Prophylaxis for TFR is not recommended for patients who receive lenalidomide.
 - Grade 1 TFR may be treated with NSAIDs (i.e. ibuprofen 400-600 mg orally every 4-6 hours as needed).
 - TFR >/= Grade 2 may be treated with corticosteroids. Narcotic analgesics may be added as needed for pain control in subjects experiencing >/= Grade 2 tumor flare.

6. Recommended Concomitant Therapy
 - a. Subjects should receive full supportive care, including transfusions of blood and blood products, antibiotics, antiemetics, antihistamines, and allopurinol when appropriate.
 - b. Anticoagulation Consideration
 - i. Lenalidomide increases the risk of thrombotic events in patients who are at high risk or with a history a thrombosis, in particular when combined with other drugs known to cause thrombosis.
 - ii. When lenalidomide is combined with other agents such as steroids (e.g. dexamethasone, prednisone), anthracyclines (Doxil, Adriamycin) and erythropoietin the risk of thrombosis is increased.
 - iii. For this study, patients will receive one aspirin (81 mg) a day while on lenalidomide. Low molecular weight heparin may be utilized in patients that are intolerant to aspirin. Coumadin should be used with caution and close monitoring of INR.
 - iv. Patients who already have a history of deep-vein thrombosis or pulmonary embolism will receive either coumadin or low-molecular weight heparin while on lenalidomide.
 - v. If patients develop thrombosis or embolism while they are receiving aspirin prophylaxis, lenalidomide will be held, patients will be anticoagulated, and once a stable anticoagulation is achieved, patients will be restarted on the same dose of lenalidomide. Patients will then continue to receive either coumadin or low-molecular weight heparin as long as they continue to receive lenalidomide.
7. Prohibited Concomitant Therapy
 - a. Concomitant use of sargramostim (GM-CSF), other anti-cancer therapies, including radiation, thalidomide, or other investigational agents is not permitted while subjects are receiving study drug during the treatment phase of the study. Concomitant medications will be documented in the medical record but will not be entered into the case report form.

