7.0 Statistical Considerations

Overview

The primary objective of this study will be to assess the safety of lenalidomide alternating with ipilimumab in stem cell transplantation. Patients will receive lenalidomide alternating with ipilimumab for 8 cycles (lenalidomide for 21 days, then one dose of ipilimumab, then repeat lenalidomide 4 weeks later, etc.). The starting and highest allowable dose of lenalidomide in this study will be 10 mg/d. Dose reductions to 5 mg may be allowed within patient based on clinical practice. Ipilimumab is fixed at 3 mg/kg. If the starting combination of lenalidomide 10 mg/d and ipilimumab 3 mg/kg results in toxicity, as defined below in the toxicity monitoring rule, in the first 3 of 3 patients, subsequent patients will be started at a lower combination dose of lenalidomide 5 mg/d and ipilimumab 3 mg/kg.

Secondary objectives include assessing overall response rate, overall survival, progression-free survival, and the cumulative incidence of acute and chronic GVHD with the competing risk of relapse in allogeneic transplant patients.

Safety Monitoring

We expect to accrue a total of 40 transplant patients onto two arms: Autologous (N=25) and allogeneic (N=15). All patients will receive lenalidomide alternating with ipilimumab (L+I). Each transplant arm will be monitored separately using monitoring rules for toxicity. The following stopping rules and boundaries were developed using the Multc Lean Desktop application (version 2.1.0) in the Biostatistics department.

The Principal Investigator and assigned Research Nurse will review the enrolled patients monthly while on active treatment to assess adverse events and stopping rules. The Biostatistician will be consulted as necessary. The data monitoring plan will be provided by the MD Anderson IND Office. This office is responsible to monitor the protocol conduct and data entry.

Toxicity monitoring rules: Each transplant arm (either autologous or allogeneic) will be monitored separately for toxicity. If there is a high probability of observing more than a 30% toxicity rate in either arm, that arm will be stopped. Toxicity for this stopping rule will include the following, at any time during active study treatment, which is defined as the first eight cycles plus 30 days following the last dose of study drug:

- Any grade 4 hematological toxicity at least probably related to study drug that does not resolve within 2 weeks

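### Sections 4.0 and 7.0 give different step-down lenalidomide doses for creatinine clearance 30 to 60, and the visible text lists no dose levels for the reductions ordered in Section 4.3

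*Combined protocol and SAP*

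**What the plan says.** **Starting dose.** The Section 4.0 table assigns "Lenalidomide 10 mg PO daily for 21 days" above 60 mL/min and "Lenalidomide 5 mg PO daily for 21 days" for 30 to 60 mL/min. Section 3.1 admits patients down to 30 mL/min, so the second group can enrol.

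**Step-down after toxicity in the first 3 of 3 patients.** Section 4.0 gives later patients "lenalidomide 5 mg/day (or 5 mg every other day for creatinine clearance of 30 to 60 ml/min"), with ipilimumab unchanged. Section 7.0 says that "subsequent patients will be started at a lower combination dose of lenalidomide 5 mg/d and ipilimumab 3 mg/kg" and makes no renal distinction.

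**Within-patient reduction.** Seven entries of the Section 4.3 table call for one dose reduction before treatment continues; the usual wording is "implement one dose reduction and continue therapy". The tumor lysis text in the same section lets the physician go down by one dose level. Section 7.0 says: "Dose reductions to 5 mg may be allowed within patient based on clinical practice".

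**The concern.** An instruction to reduce by one step needs a list of steps, and the supplied text has none. It is also unclear whether the reduction is an instruction (Section 4.3) or a permission (Section 7.0).

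The step-down matters more because it is a safety measure. It is triggered when every one of the first three patients has toxicity, and the monitoring rule then restarts at what is called a lower combination. If one renal group keeps its dose under one section and has it lowered under the other, two investigators following the protocol in good faith would treat the same patient differently. The toxicity estimate after the reset would also not describe a single, known regimen.

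**Working it through.** The plan gives no figure to reproduce. The check sets the passages side by side.

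**1. Step-down by clearance group**

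| Clearance (mL/min) | Start, Section 4.0 | After step-down, Section 4.0 | After step-down, Section 7.0 |
|---|---|---|---|
| Above 60 | 10 mg daily | 5 mg daily | 5 mg daily |
| 30 to 60 | 5 mg daily | 5 mg every other day | 5 mg daily |

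The sections agree in the first row and disagree in the second. Per 21-day course:

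- Above 60, both sections: 21 × 10 = 210 mg falls to 21 × 5 = 105 mg.
- 30 to 60, Section 7.0: 21 × 5 = 105 mg before and after, so no change.
- 30 to 60, Section 4.0: 105 mg falls to 11 × 5 = 55 mg, if dosing starts on day 1 and the course stays at 21 days. Section 4.0 does not restate the course length for this dose, so 21 days is an assumption.

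The two versions therefore differ by a factor of 105 / 55 ≈ 1.9 for this group.

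**2. How often the step-down would occur.** With independent patients and true toxicity rate p, the chance that the first three in an arm all have toxicity is p³. At p = 0.3 it is 0.027; at p = 0.5 it is 0.125. It is uncommon at the target rate and more likely when the regimen is too toxic, which is when the rule is needed.

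**3. Is a next lower dose named for a within-patient reduction?**

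1. Clearance above 60, on 10 mg daily: yes, 5 mg (Section 7.0).
2. Clearance above 60, already reduced to 5 mg, with a further event: none named.
3. Clearance 30 to 60, started on 5 mg daily: none named as a within-patient step. Section 4.0 mentions 5 mg every other day for this group, but only as a starting dose after the step-down.
4. Clearance above 60, started on 5 mg daily after the step-down: none named.
5. Clearance 30 to 60, started on 5 mg every other day under Section 4.0: none named.

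A step is expressly defined in 1 of 5 states.

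**4. Does the restart dose matter for the primary endpoint?** The seven entries are compared with the Section 7.0 stopping-rule definition.

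- Grade 3 rash, grade 3 neuropathy, grade 3 allergic reaction, and hepatic or other non-hematologic toxicity of grade 3 or more: these already count if judged at least probably drug-related. What is given later cannot change that patient's status.
- Neutropenia: grade 3 with fever is below the grade 4 hematological criterion, and grade 4 that resolves within 2 weeks is excluded from it.
- Thrombocytopenia: grade 4 that resolves within 2 weeks is excluded in the same way.
- Arrhythmia: grade 2 is below the grade 3 threshold.

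So three of the seven entries can trigger a reduction in a patient who does not yet count. For those patients the restart dose can influence whether they count later. This treats febrile neutropenia as a hematological event and not as an organ toxicity.

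**The case against.** The best defence is that Section 7.0 is an overview and the operative rules are in Sections 4.0 and 4.3. On that view its permissive sentence and its shorter step-down wording are loose summary. This has some force for the contrast between instruction and permission. It has less for the step-down dose, because Section 7.0 is where the reset of the monitoring rule is specified and nothing there says that Section 4.0 takes precedence.

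A second defence is that a list of levels may exist. Numbering in Section 4.3 goes from item 2 to item 4, the asterisks on the cytopenia entries have no visible footnote, and the package insert in Appendix F is not in the supplied text. This stands. The finding on levels is limited to the text supplied. It does not affect the step-down conflict.

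Several stronger readings are tempting, and the documents do not support them:

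- A reader might infer that the ordered reduction is impossible for every patient with clearance 30 to 60. Section 7.0 does not call 5 mg the only or lowest dose, and Section 4.0 names a lower one for exactly this group. The step is undefined, which is a weaker statement.
- A reader might infer that each such event forces a reduction. For isolated neutropenia the table allows growth factor with the dose kept, and the tumor lysis reduction is discretionary.
- A reader might infer that the primary toxicity rate as a whole depends on the restart dose. Four of the seven entries normally count before any reduction is considered.
- A reader might infer that recalculating clearance before Cycles 3, 5 and 7 returns a reduced patient to 10 mg. No passage orders this. The text is silent and needs only a clarifying phrase.
- A reader might infer from the shorter cell in the 30 to 60 row ("Ipilimumab 3 mg/kg IV x 1 dose (given 1-3 days after the last dose of lenalidomide") that this group has no rest period. The Section 4.0 prose gives the 4 weeks without renal distinction.

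**Conclusion.** The point holds in two parts of unequal certainty.

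The first is a contradiction in visible text. After the step-down, Sections 4.0 and 7.0 give different lenalidomide doses for clearance 30 to 60, and the Section 7.0 dose is the one that group starts on. The difference is about twofold per course, assuming a 21-day course. It has effect only if an arm steps down.

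The second is a gap. The reduction ordered in Section 4.3 has no stated next step for any patient on 5 mg daily or less. This is conditional on no list having been lost in extraction or placed in an appendix. It affects only patients who have a qualifying event at that dose. The documents do not give the share of patients with clearance 30 to 60, so no count is offered.

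The effect on the primary endpoint is confined to events that trigger a reduction without already counting as toxicity. With 25 and 15 patients and monitoring after each one, a single change of status can matter. No opinion is given on which dose or rule is right.

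**What to change.** - Make Sections 4.0 and 7.0 state the same step-down combination for each clearance group.
- Have Sections 4.3 and 7.0 refer to one common set of lenalidomide dose levels. It should say what applies when a reduction is ordered at the lowest level, and whether reductions are required or optional. If such a list already exists in a footnote or appendix, a cross-reference is enough.
- As a clarification, add a phrase on how a toxicity reduction relates to the clearance recalculated before Cycles 3, 5 and 7.

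The sponsor chooses the levels and the rules. The change is to protocol wording only and adds no patients, visits or data. The downside is slightly less investigator discretion.
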